Amendment 3: The protocol has been amended to remove that the device can be applied before leaving the clinic and started at home. The device should be applied and started without delay according to the Instructions for Use. It specifies that the initial dose of the study product may be administered in the clinic or at home on the day of enrollment.

Amendment 4: The protocol has been amended to clarify primary endpoint change in NT-proBNP from baseline at Day 7 and add AEs and add secondary endpoint of % Lung Fluid Measurement via Remote Dielectric Sensing (ReDS). It also includes recording device issues, removes Adverse Reaction and Suspected Adverse Reaction definitions, defines AEs of Special Interest, updates statistical analysis, increases number of subjects from 50 to 51 and minor administrative changes.

Amendment 5: The protocol has been amended to add a NT-proBNP assessment on Day 3 clinic visit, clarify 51 subjects will be included, remove the upper age limit of 80 years from inclusion criteria and align populations for analysis with the statistical analysis plan.

| Version | Date | Page | Change | Reason for Change |
|-------------|-------------|--|--|---|
| Original | 25 Jun 2020 | N/A | Original Version | New Document |
| Amendment 1 | 04 Nov 2020 | Synopsis, Subject Population p. 9, Section 4.2 Exclusion Criteria p. 24. | Added “IV” bumetanide in exclusion criteria. | Added “IV” to specify bumetanide administration route. |
| Amendment 1 | 04 Nov 2020 | Synopsis, Study Assessments and Procedures p. 10, Section 1.2.3 Risk Management p. 18. | Added “or designee”. | Added “or designee” to include additional site staff can be designated to make phone calls. |
| Amendment 1 | 04 Nov 2020 | Section 6.2 p. 28, Section 6.2.5 p. 31, Section 11.1 Appendix 1: Time and Events Schedule p. 52. | Added “If Day 3 falls on a Saturday or Sunday, subjects may be seen in the clinic and have Day 3 assessments completed on either Day 2 (Friday, if Day 3 falls on Saturday) or Day 4 (Monday, if Day 3 falls on Sunday). On Day 3 the subject will have a phone call visit.” | Added to clarify scheduling of weekend visits. |
| Amendment 1 | 04 Nov 2020 | Section 6.2.2 p. 30. | Added “study staff will” dispense additional doses of Furoscix and removed “Days 1, 2 and 3.” | Updated dose dispensing on Day 0 does not include doses for Days 1, 2, and 3. Subject returns to clinic |

| | | | | |
|-------------|-------------|---|--|--|
| | | | | on Day 1 for dose evaluation. |

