| Amendment 4 | 30 Apr 2021 | Synopsis, Study Design & Duration, p. 10, Number of Subjects, p. 11, Section 3.1, p. 20 | Increased number of subjects from 50 to 51. | Increased subject number to preserve 2:1 ratio for randomization. |
| Amendment 4 | 30 Apr 2021 | Synopsis, Statistical Analysis, p. 13 Section 8.1 – 8.3, p. 44 – 45, Section 8.4.1, p. 45, Section 8.4.2, p. 46 | Updated statistical analysis description. | Updated to provide general description of statistical analysis noting details SAP. |
| Amendment 4 | 30 Apr 2021 | Abbreviations, p. 17 | Added abbreviations for AESI, ITT, MITT, PP, ReDS, SAP. | Updated to include new abbreviations. |
| Amendment 4 | 30 Apr 2021 | Section 7.2. p. 41, Section 7.3. p. 41 | Removed Definition of Adverse Reaction and Suspected Adverse Reaction. | All AEs will be collected and assessed if IP caused the adverse event. |

| | | | | |
|-------------|-------------|---|--|---|
| Amendment 4 | 30 Apr 2021 | Section 7.3. p. 41, Section 8.6. p. 46 | Added Adverse Events of Special Interest definition and analysis. | Clarified Adverse Events of Special Interest and included in safety analysis. |
| Amendment 5 | 09 Dec 2021 | Synopsis, Study Design & Duration, p. 11, Study Assessments and Procedures, p. 14, Section 3.1, p. 21, Section 6.2. p. 30, Section 6.2.5, p. 33, Section 6.2.12, p. 37 Time and Events Schedule, p. 54-55 | Added to Day 3 clinic visit NT-proBNP assessment and specified when NT-proBNP conducted. | Updated to explore change in NT-proBNP from baseline at Day 3 as well as Day 7 and clarify NT-proBNP assessments. |
| Amendment 5 | 09 Dec 2021 | Synopsis, Study Design & Duration, p. 11, Number of Subjects, p. 12, Section 3.1, p. 21 | Removed "Up to 51" and "evaluable" description for number of study subjects. | Updated to clarify 51 subjects will be included in the study. |
| Amendment 5 | 09 Dec 2021 | Synopsis, Subject Population, p. 12-13, Section 3.1, p. 21, Section 4.1, p. 25 | Removed "80" years from age limit and replaced with "18 years or older". | Updated to remove the upper age limit. |

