| Amendment 5 | 09 Dec 2021 | Synopsis, Statistical Analysis, p.14-15, Section 8.2, p. 46, Section 8.4.2, p. 47 | Identified populations for primary endpoints. Added "who received at least 1 dose of the Investigational Product" to the definition of the Safety population. Removed the MITT (Modified Intent to Treat population). Modified the Per-Protocol population definition to specify received "at least one dose" of the Investigational Product, "completed the Day 30 clinic visit assessments AND have a Day 7 NT-proBNP value available for analysis". | Updated to align populations for analysis with the statistical analysis plan. |

PROTOCOL APPROVAL PAGE

| | |
|---|--|
| Study Title: | A Multicenter, Randomized, Open Label, Controlled Study Evaluating the Effectiveness and Safety of Furoscix On-Body Infusor vs Continued Medical Therapy for Worsening Heart Failure |
| Protocol Number: | scP-01-008 |
| Original Protocol Date of Issue: | 25 June 2020 |
| Amendment 1 Date: | 04 November 2020 |
| Amendment 2 Date: | 08 December 2020 |
| Amendment 3 Date: | 10 February 2021 |
| Amendment 4 Date: | 30 April 2021 |
| Amendment 5 Date: | 09 December 2021 |
| Sponsor Name and Address: | scPharmaceuticals, Inc. [name] [name] |

I, the undersigned, have read and approve this protocol and agree on its content. It is confirmed that the information and guidance given in this protocol complies with scientific principles, the guidelines of Good Clinical Practices, the Declaration of Helsinki in the latest relevant version, and the applicable legal and regulatory requirements.

| Approval Section | | |
|----------------------------------|---|--|
| | Name/Title | Signature / Date |
| Reviewed and Approved by: | [name], Pharm D SVP, Clinical Development and Medical Affairs | Approvals obtained through MasterControl |
| Reviewed and Approved by: | [name] Associate Director, Clinical Operations | Approvals obtained through MasterControl |
| Reviewed and Approved by: | [name] VP, Program Management and Regulatory Affairs | Approvals obtained through MasterControl |
| Reviewed and Approved by: | [name] VP, Quality | Approvals obtained through MasterControl |

INVESTIGATOR PROTOCOL AGREEMENT

Protocol Title: A Multicenter, Randomized, Open Label, Controlled Study Evaluating the Effectiveness and Safety of Furoscix On-Body Infusor vs Continued Medical Therapy for Worsening Heart Failure

By my signature, I

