## 14. ANALYSIS POPULATIONS

**Intent-to-Treat (ITT):** ITT population will include all randomized subjects. The subjects in ITT population will be analyzed according to the treatment group they were originally randomized.

**Safety:** Safety population will include all randomized subjects who received at least one dose of Investigational Product (IP). The subjects in the Safety population will be analyzed and presented according to the actual treatment received.

**Per-Protocol (PP):** All randomized subjects who received at least one dose of the IP, completed the 30 Day clinic visit assessments and have a Day 7 NT-proBNP value available for analysis.

All effectiveness analyses, including the primary endpoint and baseline characteristics will be performed on the ITT and Per-Protocol populations. Safety analyses will be performed on the safety population.

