A -1/0/1 score is created for Patient B vs. every other patient in the study, so if there are  $n$  total patients in the study, then patient B is assigned  $n$  -1/0/1 scores (including, for completeness, a score of 0 when patient B is compared to themselves). Similarly, every other patient in the study is also assigned  $n$  -1/0/1 scores.

For each patient  $i$ , the sum of all -1/0/1 scores assigned to that patient is calculated and is denoted as  $U_i$ . If  $n1$  and  $n2$  are the number of patients in the experimental and control arms, respectively, then the lowest possible value of  $U_i$  that a given patient can experience is  $-(n1 + n2 - 1)$ , which is achieved if the given patient scored a -1 versus all other  $(n1 + n2 - 1)$  patients in the study; similarly, the largest possible of  $U_i$  that a given patient can experience is  $+(n1 + n2 - 1)$ .

The numerator of the estimate of  $T$  (the Finkelstein-Schoenfeld test statistic) is the sum of the  $U_i$  across patients assigned to the experimental treatment. i.e.,

$$\sum_{i=1}^n D_i U_i$$

where  $U_i$  is the sum of the -1/0/1 scores for the  $i^{\text{th}}$  patient in the sample,  $D_i$  is the indicator of the treatment group to which the  $i^{\text{th}}$  patient was randomized ( $D_i = 0$  for control and  $D_i = 1$  for experimental) and  $n$  is the total sample size.

The denominator of  $T$  is:

$$\sqrt{\frac{n1 * n2}{n * (n - 1)} \sum_{i=1}^n U_i^2}$$

where (a)  $n1$  and  $n2$  are the number of patients in the experimental and control arms, respectively; (b)  $n$  is the total sample size ( $= n1 + n2$ ); and (c)  $U_i$  is the sum of the -1/0/1 scores for the  $i^{\text{th}}$  patient in the sample. The test statistic follows a standard normal distribution; the two-sided p-value is the area in the upper and lower tails of  $T$  on the standard normal curve.

The primary efficacy endpoint will be repeated for the ITT and PP analysis populations using the Day 3 NT-proBNP value (instead of the Day 7 NT-proBNP value). The Day 3 NT-proBNP value will be used for calculating the percent change from baseline as follows:

- Percent Change in NT-proBNP from baseline at 3 days:
  - if Patient A's change from baseline at 3 days in NT-proBNP < Patient B's change from baseline at 3 days in NT-proBNP, then score = -1 for Patient B
  - if Patient A's change from baseline at 3 days in NT-proBNP > Patient B's change from baseline at 3 days in NT-proBNP, then score = +1 for Patient B

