#### **15.2.1.1 INDIVIDUAL ANALYSIS OF PRIMARY ENDPOINTS**

Each component of the primary efficacy endpoint will be analyzed individually for the ITT and PP populations between treatment groups.

- CV death at 30 days:

CV death will be summarized by counts and percentages for Furoscix on-body Infusor and Continued medical therapy.

In addition, comparison of the proportion of death among Furoscix on-body Infusor and Continued medical therapy will be conducted using chi-square test. Proportion of death in each treatment group and also the proportion difference along with its corresponding 95% CI and p-value will be presented at Day 30.

If any of the cells has expected frequency count less than 5 then the comparisons will be performed through a Fisher exact test. The p-value will also be presented using Chi-square/Fisher exact test to identify statistically significant differences in proportion of deaths for Furoscix on-body Infusor vs Continued medical therapy.

- HF hospitalization at 30 days:

The analysis of HF hospitalization will be conducted similar to CV death at 30 Days.

- Urgent ED/Clinic visit at 30 days for WHF (defined as IV diuretics, augmentation of or new administration of metolazone):

The analysis of Urgent ED/Clinic visit for worsening heart failure will be conducted similar to CV death at 30 Days.

- Percent Change from baseline in NT-proBNP at Day 3, at Day 7 and at Day 30:

The percent change in NT-proBNP from baseline across timepoints will be analyzed using a GEE model which includes change in NT-proBNP from baseline as the response variable, treatment, timepoint and treatment by timepoint interaction as fixed effects and baseline value of NT-proBNP as the covariate. An unstructured covariance matrix structure will be used to model the within subject errors. Least square means, corresponding 95% Confidence Interval (CI) and standard error (SE) from the model will be presented for Furoscix on-body Infusor and Continued medical therapy. The LS means estimate, standard error, 95% CI, and p-value for the treatment difference will also be presented.

Additionally, non-parametric correlation (Spearman's Rank) analysis of percent change from baseline in NT-proBNP at Day 3, 7 and 30 and number of doses (Infusion) will be performed. The significance of correlation coefficient will be tested using a t-test.

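### If anyone was randomized before Amendment 5, the Day 3 and Day 7 composites rest on different subjects, and the SAP has no Day 7 run on the subjects scheduled for Day 3

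*SAP*

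**What the plan says.** - **When the draw began.** The protocol's introductory account of Amendment 5 lists these changes together: "add a NT-proBNP assessment on Day 3 clinic visit, clarify 51 subjects will be included, remove the upper age limit of 80 years". The change table has the entry "Added to Day 3 clinic visit NT-proBNP assessment and specified when NT-proBNP conducted" and gives the reason: "Updated to explore change in NT-proBNP from baseline at Day 3 as well as Day 7". The age entry reads "Updated to remove the upper age limit". The approval page dates the amendment "09 December 2021".
- **Who is analysed.** SAP 15.2.1 says: "The primary efficacy endpoint will be repeated for the ITT and PP analysis populations using the Day 3 NT-proBNP value". Under SAP 14, "ITT population will include all randomized subjects". The per-protocol set requires a Day 7 NT-proBNP value but not a Day 3 value.
- **The time course.** SAP 15.2.1.1 analyses "Percent Change from baseline in NT-proBNP at Day 3, at Day 7 and at Day 30" in one GEE model, with baseline as covariate and an unstructured covariance. It also correlates each day's change with the number of doses.
- **Missing values.** SAP 8 and 15 rule out imputation. SAP 15.2.1 gives a score of 0 for a tie on NT-proBNP. It gives no score for a pair in which one value is absent.

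The amendment log is used here only as a history of when sampling began, not as a conflict with the current text.

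**The concern.** Exploring Day 3 as well as Day 7 is the stated reason for the extra sample, and refining pivotal endpoints is a secondary objective (SAP 6.2). Readers will therefore set the Day 3 composite beside the Day 7 composite. If some subjects were randomized before the draw existed, the two results do not rest on the same subjects. Day 3 could then appear the poorer endpoint because of the sampling schedule alone. Those with a Day 3 value may also differ in kind, because the same amendment opened entry to patients over 80. Nothing in the SAP identifies who was scheduled for Day 3 or repeats Day 7 in those subjects.

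**Working it through.** **1. The plan's own figure.** 51 × 2/3 = 34 and 51 × 1/3 = 17, as SAP 4 states. SAP 4 reports no power analysis, so the documents supply no effect size or SD. The effect sizes, event rates and enrolment splits below are assumptions.

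**2. Pairs that Day 3 can decide.** Let m be the number randomized before Day 3 was scheduled, assumed to split 2:1. The Day 3 sets are 34 − 2m/3 and 17 − m/3. The between-arm pairs with both values are the product of these, out of 34 × 17 = 578.

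| m | Day 3 sets | Pairs | Share of 578 |
|---|---|---|---|
| 0 | 34, 17 | 578 | 100% |
| 9 | 28, 14 | 392 | 68% |
| 18 | 22, 11 | 242 | 42% |
| 27 | 16, 8 | 128 | 22% |
| 36 | 10, 5 | 50 | 9% |

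**3. Effect on the FS statistic.** The SAP 15.2.1 statistic was simulated 3000 times per case. Assumptions: the same 0.8 SD effect on both days, correlation 0.7 between days, 10% of each arm with an event, and no difference between eras. Entries are mean z.

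| m | Day 7, all 51 | Day 3, missing pairs score 0 | Day 3, earlier subjects dropped | Day 7, same remaining subjects |
|---|---|---|---|---|
| 0 | 2.04 | 2.04 | 2.06 | 2.04 |
| 9 | 2.06 | 1.68 | 1.83 | 1.84 |
| 18 | 2.02 | 1.26 | 1.62 | 1.62 |
| 27 | 2.02 | 0.80 | 1.37 | 1.36 |
| 36 | 2.03 | 0.37 | 1.08 | 1.09 |

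Power at two-sided 0.05 is about 56% at m = 0. At m = 18 the Day 3 power is 24% if missing pairs score 0 and 37% if earlier subjects are dropped. At m = 36 it is 7% and 16%. The mean Day 3 arm difference stays near −0.80 SD throughout, so what falls is information, not the effect.

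A second set of assumptions gives the same pattern: 0.6 SD effect, CV death 2%, HF hospitalization 10%, urgent visit 10%, missing pairs scored 0. Mean z is about 1.22 at Day 7. At Day 3 it is 0.80, 0.44 and 0.12 when 25%, 50% and 75% of subjects are earlier. On matched subjects the two days agree: 1.05 and 1.05, 0.87 and 0.85, 0.60 and 0.60.

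**4. Effect of an era difference.** A shift common to both arms cancels from the treatment difference. With an assumed 0.5 SD shift, a 0.6 SD effect and 25%, 50% or 75% earlier, the simulated arm differences were −0.61, −0.61 and −0.60 at Day 3, against −0.59, −0.60 and −0.60 at Day 7. Within-arm raw means do move between days, by m/51 times the shift.

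If the treatment effect itself differs between eras by Δ, the raw Day 3 minus Day 7 gap is (m/51) × Δ. With Δ = 0.4 SD assumed:

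- m = 18: 18/51 × 0.4 = 0.14. Simulated: Day 7 −0.667, Day 3 −0.805. An estimate that borrows from Day 7 through the correlation, as an unstructured model does, is −0.713, leaving 0.713 − 0.667 = 0.046.
- m = 36: 36/51 × 0.4 = 0.28. Simulated: −0.513 and −0.793. The borrowing estimate is −0.597, leaving 0.597 − 0.513 = 0.084.

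**The case against.** The strongest objection is that the premise is not in the documents. They give no first-subject date and no enrolment count. Amendment 5 came about 17 months after the original protocol (25 Jun 2020) of a study planned to last 9 months. That makes earlier enrolment plausible but does not establish it, because nothing says when the 9 months began. This stands, so the point is conditional.

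A reader might also infer that Day 3 versus Day 7 differences reflect enrolment era, or that the Day 3 comparison is confounded. The documents do not support either. Treatment is randomized within each era. The fall in z in step 3 was produced with no era effect at all: it comes from Day 3 values that were never scheduled. Its size also depends on the score for a missing pair, which the SAP does not state. Dropping the earlier subjects shrinks the loss but does not remove it.

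Nor is a large time-course distortion supported. An assumed era gap of 10 to 20 points in mean percent change, with 25% to 75% earlier, gives 0.25 × 10 = 2.5 to 0.75 × 20 = 15 points. That treats each day as a raw average and ignores the baseline covariate and unstructured covariance in SAP 15.2.1.1. Only the independence fallback in SAP 7.1 would lose the borrowing between days.

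Three further points are fair:

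- The SAP specifies no separate test of Day 3 against Day 7.
- Counts of missing values by visit (SAP 7.1) and the component listing (SAP 15.2.1) would reveal a shortfall. They would not give the like-for-like result.
- The remedy is thin where the problem is largest. At 75% earlier, about 13 subjects remain (roughly 9 and 4).

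**Conclusion.** The point holds conditionally. If m > 0, the Day 3 and Day 7 composites on the full ITT and per-protocol sets are not like for like, and the Day 3 FS statistic will tend to look weaker for an identical drug effect. Under the 0.8 SD assumptions with 18 earlier subjects, mean z falls from 2.02 to 1.26 or 1.62, depending on how those subjects are handled. Matching the subjects removes the gap in every case simulated. Within-arm means can also shift between days, and so can treatment differences if the effect varies by era. The unstructured model reduces this second shift. The Day 3 arm comparison itself remains randomized. At m = 0 nothing needs changing. This is a modest improvement to a supplementary analysis in an exploratory pilot.

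**What to change.** - **SAP 15.2.1.** Define a flag for subjects randomized with Day 3 NT-proBNP scheduled. Take it from the protocol version in force at the site at randomization, because Protocol 9.1.2 requires ethics approval before an amendment is implemented and a single calendar date may misclassify. Run the Day 3 composite on flagged ITT and per-protocol subjects, and report the Day 7 composite on the same subjects beside it.
- **SAP 15.2.1.1.** Keep the Day 7 and Day 30 estimates on all subjects. Take any statement comparing Day 3 with Day 7 or Day 30 from a repeat of the NT-proBNP model in flagged subjects.
- **Tables.** Footnote every Day 3 table with the number scheduled, by arm.
- **Small subsets.** If most subjects preceded Amendment 5 (about 13 flagged at 75%), present the Day 3 work descriptively only.

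The cost is SAP wording, one derived flag and reruns of existing programs. The downside is that Day 3 openly rests on fewer subjects. The main Day 7 analysis does not change.

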#### **15.2.1.1 INDIVIDUAL ANALYSIS OF PRIMARY ENDPOINTS**

Each component of the primary efficacy endpoint will be analyzed individually for the ITT and PP populations between treatment groups.

- CV death at 30 days:

CV death will be summarized by counts and percentages for Furoscix on-body Infusor and Continued medical therapy.

In addition, comparison of the proportion of death among Furoscix on-body Infusor and Continued medical therapy will be conducted using chi-square test. Proportion of death in each treatment group and also the proportion difference along with its corresponding 95% CI and p-value will be presented at Day 30.

If any of the cells has expected frequency count less than 5 then the comparisons will be performed through a Fisher exact test. The p-value will also be presented using Chi-square/Fisher exact test to identify statistically significant differences in proportion of deaths for Furoscix on-body Infusor vs Continued medical therapy.

- HF hospitalization at 30 days:

The analysis of HF hospitalization will be conducted similar to CV death at 30 Days.

- Urgent ED/Clinic visit at 30 days for WHF (defined as IV diuretics, augmentation of or new administration of metolazone):

The analysis of Urgent ED/Clinic visit for worsening heart failure will be conducted similar to CV death at 30 Days.

- Percent Change from baseline in NT-proBNP at Day 3, at Day 7 and at Day 30:

The percent change in NT-proBNP from baseline across timepoints will be analyzed using a GEE model which includes change in NT-proBNP from baseline as the response variable, treatment, timepoint and treatment by timepoint interaction as fixed effects and baseline value of NT-proBNP as the covariate. An unstructured covariance matrix structure will be used to model the within subject errors. Least square means, corresponding 95% Confidence Interval (CI) and standard error (SE) from the model will be presented for Furoscix on-body Infusor and Continued medical therapy. The LS means estimate, standard error, 95% CI, and p-value for the treatment difference will also be presented.

Additionally, non-parametric correlation (Spearman's Rank) analysis of percent change from baseline in NT-proBNP at Day 3, 7 and 30 and number of doses (Infusion) will be performed. The significance of correlation coefficient will be tested using a t-test.

Finally, all outcomes of the primary endpoint will be summarized using descriptive statistics such as n, mean, median, minimum, and maximum for continuous variables and count and percentages will be provided for categorical variables by treatment group and overall.

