5.4. Selection of Doses in the Study

The dose of 80 mg is the fixed dose of Furoscix. This was selected based on clinical criteria and physician prescribing and is consistent with the approved labeling of furosemide injection, United States Pharmacopeia. The dosing frequency and duration of the initial therapy will be determined by the investigator based on an estimated volume of diuresis desired to transition Subject back to their oral maintenance diuretic therapy. The total duration in days and number of doses will be determined by the treating investigator based on an estimated volume of diuresis desired to transition Subject back to their oral maintenance diuretic therapy.

After Subjects have been transitioned to their oral maintenance diuretic regimen, additional doses of Furoscix can be prescribed during the 30-day study period as needed based on the presence of symptoms of congestion (dyspnea, edema, and/or excess weight gain) as determined by the investigator. No more than 7 doses of Furoscix is permitted during the 30-day study period. Additional doses beyond 7 requires approval by the medical monitor.

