### **4. SAMPLE SIZE**

Fifty-one (51) subjects will be included and randomly assigned in a 2 to 1 ratio to receive Furoscix (n=34) or continued medical therapy (n=17) in the home setting with 30 days of follow-up. Given the exploratory nature of this study, no formal power analysis of sample size was conducted.

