## 15. STATISTICAL ANALYSIS

This is a multicenter, randomized, open label, controlled study evaluating the effectiveness and safety of the Furoscix Infusor versus continued medical therapy in patients with chronic heart failure and fluid overload requiring augmentation in diuretic therapy outside of the acute care setting. The SAP takes precedence over the protocol.

Unless otherwise specified, all baseline data, including demographic data and other clinical characteristics will be compared using descriptive statistics grouped by treatment group (Furoscix On-Body Infusor vs Continued Medical Therapy for Worsening Heart Failure). Change from baseline is the absolute change, unless stated otherwise; which then will be percentage change from baseline. Tables will include footnotes indicating definition implemented. Continuous data will be summarized by reporting the number of observations, mean, standard deviation, minimum, median, and maximum values. Categorical data will be described using frequency tables showing the number and percentage of subjects falling within a particular category. Shift tables will be given where appropriate to show change at follow-up compared to baseline values.

Between-group analyses of baseline characteristics will employ descriptive statistics. Mortality and morbidity events will be assessed using appropriate statistical tests. The primary endpoint will be compared between treatments using the Finkelstein-Schoenfeld Method, comparing components of the composite endpoint between patients hierarchically. Given the nature of the study, there will be no imputation of missing data on endpoints.

The primary endpoints including CV death at 30 days, HF hospitalization at 30 days, Urgent ED/Clinic visit at 30 days for WHF (defined as IV diuretics, augmentation of or new administration of metolazone), and change in NT-proBNP from baseline at 7 days will also be summarized and analyzed separately.

In general, secondary efficacy with follow-up timepoints will be analyzed using Generalized Estimating Equations (GEE) models.

Statistical tests will be performed at a two-sided alpha level of 0.05, unless otherwise specified. Given the nature of the study, there will be no adjustment for multiple comparisons.

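### The correlation of NT-proBNP change with number of doses does not limit the count to infusions before each sample, and dosing follows response, so a significant coefficient can arise with no dose effect

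*SAP*

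**What the plan says.** SAP 15.2.1.1 adds a supplementary analysis to the NT-proBNP component: a Spearman rank "analysis of percent change from baseline in NT-proBNP at Day 3, 7 and 30 and number of doses (Infusion) will be performed". It continues: "The significance of correlation coefficient will be tested using a t-test". SAP section 15 sets the level ("Statistical tests will be performed at a two-sided alpha level of 0.05, unless otherwise specified") and leaves the tests unadjusted ("Given the nature of the study, there will be no adjustment for multiple comparisons"). The subsection opens by naming its populations: "Each component of the primary efficacy endpoint will be analyzed individually for the ITT and PP populations between treatment groups". Nothing there says which infusions count for which sampling day, whether control subjects are included, or how the coefficient is to be read.

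Dose number is not randomised. Protocol 5.4 says that the "number of doses will be determined by the treating investigator based on an estimated volume of diuresis desired". Protocol 6.2.3 to 6.2.6 have the site review clinical response on Days 1 to 6 and alter treatment accordingly. SAP section 2 allows further infusions for congestion symptoms during the 30 days, with a ceiling of seven unless the medical monitor agrees to more.

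On sample size, SAP section 4 gives 34 Furoscix and 17 control subjects, calls the study exploratory, and states that "no formal power analysis of sample size was conducted".

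**The concern.** Two separate things can produce a correlation that owes nothing to what the infusions do.

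- **Time order.** If the count is the subject's total, an NT-proBNP change measured on Day 3 or Day 7 is correlated partly with infusions that had not yet been given.
- **Indication.** A subject who stays congested is likely to have both a smaller fall in NT-proBNP and more infusions. Congestion then drives both variables. This applies even to infusions given before the sample.

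This is the only analysis in the SAP that relates dose number to NT-proBNP, and a p-value is attached to it. At stake is how that p-value is read. It could be taken as evidence about dose and response when it reflects who was given more doses, or indication could mask a real relation.

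**Working it through.** **1. Time order, from the documents.**

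| Sample | Infusions that can come after it |
|---|---|
| Day 3 | One later that day (Protocol 6.2 wants visits early to leave room for the 5-hour infusion); Days 4–6, for which product is handed out at this visit (Protocol 6.2.5); later as-needed doses |
| Day 7 | As-needed doses up to Day 29 (Protocol 6.2) |
| Day 30 | None: the treatment phase has ended and unused product is collected at the visit (Protocol 6.2.9) |

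Time order is therefore a problem for Days 3 and 7 only. Indication applies to all three days.

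**2. The plan's own figures.** 51 × 2/3 = 34 and 51 × 1/3 = 17, as SAP section 4 states. No expected correlation or power is given. The test is t = r√[(n−2)/(1−r²)], so the critical value is |rho| = t/√(t²+n−2).

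- n = 34: t(0.975; 32 df) = 2.037, so |rho| = 2.037/√(4.149+32) = 0.339.
- n = 51: t(0.975; 49 df) = 2.010, so |rho| = 0.276.

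Three independent unadjusted tests would give 1 − 0.95³ = 14.3% for at least one false positive. These three share a dose variable, so this is only a guide.

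**3. Is the test itself sound?** Assumed model: a standard normal dosing need is cut at its sevenths into 1–7 doses and has correlation c with NT-proBNP change. Doses have no effect. There are 34 subjects and 20,000 runs per value.

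| c | 0 | 0.1 | 0.2 | 0.3 | 0.4 | 0.5 | 0.6 |
|---|---|---|---|---|---|---|---|
| Rejected at 0.05 | 5.1% | 7.9% | 18.9% | 36.4% | 60.0% | 81.8% | 94.8% |

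With no link the test keeps its level despite tied dose counts. What matters is the meaning of the dose variable.

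**4. What a pre-sample window does.** Assumed model, with no effect of any dose:

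- Daily congestion follows X(t) = 0.93·X(t−1) + noise, with unit variance.
- Perceived need is r·X plus noise.
- An infusion is given on Day 0, on Days 1–6 if need exceeds 0.2, and on Days 7–29 if it exceeds 1.8, capped at seven.
- NT-proBNP change on the sampling day is λ·X plus noise.

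Mean total doses were 4.0 to 4.3. There were 34 subjects and 5,000 runs per case. Cells show the rejection rate, with mean rho in brackets where one link strength applies. The prior count runs to the day before the sample.

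| Links r / λ | Day 3, total | Day 3, prior | Day 7, total | Day 7, prior | Day 30 |
|---|---|---|---|---|---|
| 0 / 0.3–0.7 | 4.3–5.3% | 4.9–5.3% | 4.8–5.2% | 4.9–5.4% | 4.8–5.3% |
| 0.3 / 0.3 | 11.5% (0.13) | 7.9% (0.08) | 11.5% (0.13) | 10.1% (0.11) | 5.5% (0.05) |
| 0.5 / 0.5 | 46.6% (0.31) | 25.8% (0.23) | 41.4% (0.30) | 37.0% (0.28) | 10.3% (0.12) |
| 0.7 / 0.7 | 89.2% (0.51) | 71.7% (0.42) | 84.0% (0.48) | 81.7% (0.46) | 18.0% (0.18) |

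In the middle row the window removes 46.6 − 25.8 = 20.8 points at Day 3, but only 41.4 − 37.0 = 4.4 points at Day 7. Day 30 is low because most modelled doses fall in the first week and congestion then decorrelates (0.93²⁴ ≈ 0.18 from Day 6 to Day 30). That is a property of the assumed persistence.

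**5. Controls.** Adding 17 controls at zero doses to the model of step 3, with no treatment effect, gives 5.2% at c = 0, 14.3% at 0.3 and 30.8% at 0.5, against 36.4% and 81.8% without them for the last two. Controls dilute this artefact. If the treatment does lower NT-proBNP, they also bring the between-arm difference into rho with a negative sign, so the coefficient mixes two quantities. The populations differ too: ITT contains the controls, while PP (SAP section 14) requires a dose of investigational product and, read literally, leaves them out.

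**The case against.** The case on the other side is substantial.

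- **The SAP does not say that later doses are counted.** This is correct. A reader might infer that the total is used, because one unindexed count serves three days. That is the natural reading, but the text leaves the window undefined, and undefined is all that can be claimed.
- **The SAP plans a correlation and does not call it dose-response.** Also correct. If dosing tracks response, an association exists and rejecting is right. A reader might infer that the t-test is faulty, but it is not. The problem is that the SAP gives no caution about reading an association as an effect of dose.
- **Protocol 5.4 describes intended diuresis, not response.** True of that sentence: planned need alone could give either sign. The response-driven part comes from the daily reviews in Protocol 6.2.3 to 6.2.6 and the as-needed rule in SAP section 2. A positive sign is therefore plausible but assumed.
- **Controls may never have been intended to enter.** An infusion count applies naturally to the Furoscix arm. Their inclusion is unspecified, and step 5 does not show that it worsens the artefact.
- **The consequence is limited.** A reader might infer that pivotal dosing would be misdirected. No text ties this correlation to a dosing decision. The study is an unpowered pilot that claims no multiplicity control.
- **A confidence interval carries much the same inference as the t-test.** This stands, so the explicit caveat on interpretation has to do most of the work.

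**Conclusion.** The concern holds as a minor point. The dose count has no window and no stated arm. Infusions can follow the Day 3 and Day 7 samples, and dosing is adjusted to response, so rho can be non-zero with no dose effect.

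With the total count, the rejection rate at Days 3 and 7 runs from 11.5% through 41–47% to 84–89% as the assumed links strengthen. At Day 30 it runs from 5.5% to 18%, from confounding only. These figures rest wholly on the assumed link strengths, persistence and dosing thresholds, on 34 subjects with complete samples, and on use of the total count. They show a range and do not forecast this trial.

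A reader might extend the point to the main NT-proBNP results. The documents do not support that: the Finkelstein-Schoenfeld and GEE comparisons are by randomised arm and do not use the dose count.

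**What to change.** Amend the paragraph in SAP 15.2.1.1 to say that:

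1. for each timepoint, the dose variable is the number of infusions started before that NT-proBNP sample;
2. the analysis uses the Furoscix arm only;
3. rho is reported with a 95% confidence interval as a descriptive measure, with no t-test and no significance claim;
4. dose number is chosen by the investigator and adjusted to response, so rho is not an estimate of dose-response.

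No new dosing data are needed: the diary in Protocol 6.2.24 already records the start date and time of each infusion. Use the actual sampling date, because a weekend Day 3 visit may move to Day 2 or Day 4. The documents do not say whether the time of the blood draw is recorded; if it is not, count infusions from days before the sampling date.

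The cost is a short SAP edit, some programming and one lost p-value per timepoint. The window deals with time order but only reduces confounding by indication, so item 4 is needed even when items 1 to 3 are adopted.
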